### **7.6.14 Investigator Global Aesthetic Improvement (iGAI) Score**

The iGAI score is a 5-point scale with the following categories:

1. Worse – the appearance is worse than the original condition.
2. No change – the appearance is the same as the original condition.
3. Improved – obvious improvement in appearance from the initial condition. A touch-up might further improve the result.
4. Much improved – marked improvement in appearance from the initial condition, but not completely optimal. A touch-up might slightly improve the result.
5. Very much improved – optimal cosmetic result.

The iGAI score will be assessed by the Blinded Evaluating Investigator at Visits 2, 3, 4, and 5.

### **7.6.15 Investigator Ease of Use Assessment**

The Treating Investigator will assess overall ease of use by the device by circling the appropriate number on the numerical rating scale from 0 being not easy to 10 being most easy at Visit 1/Day 1 and for subjects who have touch-up treatment at Visit 2/Month 1.

### **7.6.16 Swelling Assessment**

Swelling will be assessed by the Blinded Evaluating Investigator at Visits 2, 3, 4, and 5 using the 5-point scale with the categories that follow. The blinded Evaluating Investigator should examine both upper and lower lip simultaneously and recall the degree of augmentation originally provided for comparison. The subject should not be specifically questioned regarding swelling but if the subject spontaneously reports it, such information can be used to assist in selection of a grade for swelling.

0: None – No swelling noticeable. Lips appear the same as when originally augmented. Any lip enlargement is due to the implanted product only.

1: Minimal – Slight enlargement of either lip beyond the originally provided augmentation. May or may not be noticeable to the subject but is noticeable to the investigator.

2: Mild – Some enlargement of either lip beyond the original augmentation that is easily noticeable to the subject, but the lips do not appear abnormally large.

3: Moderate – Significant enlargement of either lip beyond the original augmentation. Either lip appears abnormally large.

4: Severe – Any degree of swelling that substantially interferes with lip function such as changes in speech or difficulty eating or drinking.

**7.6.17 Lip Function Evaluation**

Subjects’ lip function will be assessed by the Blinded Evaluating Investigator by their ability to sip liquid through a straw prior to any injections and at all follow-up visits.

**7.6.18 Lip Sensation Evaluation**

Subjects’ lip sensation will be assessed by the Blinded Evaluating Investigator and tested via: 1) the monofilament test (i.e., a subject’s ability to feel the sensation of a 0.4G monofilament at three points on the upper lip and three points on the lower lip and 2) the cotton wisp test (i.e., a subject’s ability to feel the sensation of a cotton wisp at three points on the upper lip and three points on the lower lip) prior to any injections and at all follow-up visits.

**7.6.19 Lip Texture Evaluation**

Subjects’ lip texture will be assessed by the Blinded Evaluating Investigator as normal or abnormal prior to any injection and at all follow-up visits.

**Table 2. Lip Texture Scoring Criteria**

Normal	Abnormal		
	Mild	Moderate	Severe
Texture of the lip is even without visible undulations or excessive coarseness beyond that expected for stated age	The lip shows a single area of textural irregularity (a small papule, area of excess smoothness, focal absence of perpendicular lines) can be visualized only with close inspection	The lip shows more than one area of textural irregularity (a small papule, area of excess smoothness, focal absence of perpendicular lines) can be visualized only with close inspection.  Or  The lip shows one area of textural irregularity (less than ¼ of the lip area) at a conversational distance.	The lip shows two or more areas of textural irregularity (a small papule, area of excess smoothness, focal absence of perpendicular lines) can be visualized at a conversational distance.  Or  The lip shows one area of textural irregularity (more than ¼ of the lip area) at conversational distance

**7.6.20 Lip Firmness Evaluation**

Subjects’ lip firmness will be assessed by the Blinded Evaluating Investigator as normal or abnormal prior to any injection and at all follow-up visits.

**Table 3. Lip Firmness Scoring Criteria**

Normal	Abnormal		
	Mild	Moderate	Severe
Lip is supple when compressed laterally and surface distorted readily with minimal pressure. Pressure with a narrow diameter instrument (cotton-tipped applicator, toothpick, etc) causes a focal depression in the surface of the lip. Upon palpation, lip is absent of abnormal structures such as scars or lumps; normal product feel without being visible.	Lip is slightly firm with lateral compression or required slightly greater than normal pressure to distort the surface. Upon palpation, an abnormal structure such as a scar or lump is felt, but is not visible.	Lip is firm with lateral compression or requires distinctly greater than normal pressure to distort the surface or pressure with a narrow diameter instrument (cotton-tipped applicator or toothpick) causes a broader depression in the surface of the lip. Upon palpation, an abnormal structure such as a scar or lump is felt and is visible.	Lip is very firm with lateral compression or requires significantly greater than normal pressure to distort the surface. Upon palpation, an abnormal structure such as a scar or lump is felt and is visually distracting.

**7.6.21 Lip Symmetry Evaluation**

Subjects’ lip symmetry will be assessed by the Blinded Evaluating Investigator as normal or abnormal prior to any injection and at all follow-up visits.

**Table 4. Lip Symmetry Scoring Criteria**

Normal	Abnormal		
	Mild	Moderate	Severe
One side of the lip balanced or mirrored the other side	One side of the lip shows a 1 mm or less difference in height or a 1 mm or less difference in the length of the vermilion at repose.	One side of the lip shows a 1.1 mm to 2 mm difference in height or a 1.1 to 2 mm difference in the length of the vermilion at repose	One side of the lip shows a greater than 2 mm difference in the height or a greater than 2 mm difference in the length of the vermilion at repose.

### 7.6.22 Lip Movement/Function

Lip movement/function will be evaluated by the Blinded Evaluating Investigator as normal or abnormal prior to any injection and at all follow-up visits as the subject's ability to pucker lips, blowing and pronunciation of words that begin with the letter "W" such as water, work, week and wind.

### 7.6.23 Subject Satisfaction with Lips (Visual Analog Scale)

Subjects will be asked to assess their overall satisfaction with their lips at Visits 2, 3, 4, and 5 using a 100-mm VAS scale from 0 = Very Unsatisfied to 100 = Very Satisfied (Figure 1).

**Figure 1. Visual Analog Scale for Subject Satisfaction**

### 7.6.24 Subject Diary Card

A diary card will be dispensed to each enrolled subject at Visit 1/Day 1. The subject will be instructed to complete the diary cards to record any AEs experienced during the 2 weeks after receiving the initial treatment and the touch up treatment. The diary cards will be collected at Visit 2/Month 1 and Visit 3/Month 2 if touch up treatment was given. A new diary card will be dispensed at Visit 2/Month 1 if touch up treatment is given.

### 7.6.25 Adverse Events and Serious Adverse Events Assessment

See Section 7.9 for instructions on the assessment and reporting of AEs and SAEs and Section 7.9.7 for instructions on reporting SAEs to the Sponsor or designee.

### 7.6.26 Treatment Question

At Visit 5 or early termination, subjects and blinded evaluating investigators will be asked to identify which treatment they thought had been administered.

## 7.7 Visit-Specific Procedures

The following sections outline the procedures required at each visit.

### 7.7.1 Visit 1/Day 1: Baseline and Treatment

- Obtain written informed consent
- Obtain medical history and demographic information, including Fitzpatrick skin type classification
- Perform abbreviated physical examination, including height, weight, and vital signs (temperature, heart rate, blood pressure, and respiratory rate)
- Vision Evaluation (Snellen visual acuity, confrontational visual fields, ocular motility)
- Obtain/record prior and concomitant medications/treatments
- Perform urine pregnancy test for all women of childbearing potential
- LFGS assessment
- POL assessment

- Lip function evaluation prior to treatment administration
- Lip sensation evaluation prior to treatment administration
- Lip texture evaluation prior to treatment administration
- Lip firmness evaluation prior to treatment administration
- Lip symmetry evaluation prior to treatment administration
- Lip movement/function evaluation prior to treatment administration
- Evaluate inclusion/exclusion criteria
- Randomization
- Treatment administration
- Vision Evaluation (Snellen visual acuity, confrontational visual fields, ocular motility) 30 minutes after treatment
- Investigator Ease of Use assessment
- Assess AEs
- Dispense subject diary card
- Schedule next visit
- Complete CRFs

**7.7.2 Telephone Contacts on Day 3 and Day 14 ( $\pm$  2 days)**

- Assess AEs
- Assess concomitant medications/treatments
- Confirm adherence to prohibited treatments/medications

**7.7.3 Visit 2/Day 28 ( $\pm$  2 days): Interim Visit at Month 1 with Possible Touch-up Treatment**

- LFGS assessments
- POL assessments
- pGAI assessment
- iGAI assessment
- Lip function evaluation prior to treatment administration if applicable
- Lip sensation evaluation prior to treatment administration if applicable
- Lip texture evaluation prior to treatment administration if applicable
- Lip firmness evaluation prior to treatment administration if applicable
- Lip symmetry evaluation prior to treatment administration if applicable
- Lip movement/function evaluation prior to treatment administration if applicable
- Vision Evaluation (Snellen visual acuity, confrontational visual fields, ocular motility)
- Swelling Assessment
- Subject satisfaction with lips (VAS)

- Treatment administration if touch-up is needed (at Treating Investigator's discretion)
- Vision Evaluation (Snellen visual acuity, confrontational visual fields, ocular motility) 30 minutes after treatment if applicable
- Investigator Ease of Use assessment if applicable
- Assess AEs
- Assess concomitant medications/treatments
- Collect subject diary card
- Dispense new subject diary card if touch up treatment is given
- Schedule next visit
- Complete CRFs

**7.7.4 Telephone Contacts on Day 33 and Day 44 ( $\pm 2$  days) for Subjects with Touch-up Treatment**

- Assess AEs
- Assess concomitant medications/treatments
- Confirm adherence to prohibited treatments/medications

**7.7.5 Visit 3/Day 56 ( $\pm 4$  days) and Visit 4/Day 84 ( $\pm 4$  days): Interim Visits at Month 2 and Month 3**

- LFGS assessments
- POL assessments
- pGAI assessment
- iGAI assessment
- Lip function evaluation
- Lip sensation evaluation
- Lip texture evaluation
- Lip firmness evaluation
- Lip symmetry evaluation
- Lip movement/function evaluation
- Vision Evaluation (Snellen visual acuity, confrontational visual fields, ocular motility)
- Assess AEs
- Swelling Assessment
- Assess concomitant medications/treatments
- Subject satisfaction with lips (VAS)
- Collect subject diary card at Visit 3 if dispensed at Visit 2
- Schedule next visit
- Complete CRFs

#### **7.7.6 Telephone Contacts on Day 112 (Month 4) and Day 140 (Month 5) $\pm$ 4 days**

- Assess AEs
- Assess concomitant medications/treatments
- Confirm adherence to prohibited treatments/medications

#### **7.7.7 Visit 5/Day 168 ( $\pm$ 7 days): Month 6 End of Study Visit/Early Termination**

- LFGS assessments
- POL assessments
- pGAI assessment
- iGAI assessment
- Lip function evaluation
- Lip sensation evaluation
- Lip texture evaluation
- Lip firmness evaluation
- Lip symmetry evaluation
- Lip movement/function evaluation
- Vision Evaluation (Snellen visual acuity, confrontational visual fields, ocular motility)
- Assess AEs
- Swelling Assessment
- Assess concomitant medications/treatments
- Subject satisfaction with lips (VAS)
- Treatment question
- Obtain written consent for open-label retreatment protocol
- Complete CRFs

All subjects will be evaluated for retreatment and undergo consent procedure for the subsequent open-label retreatment protocol.

#### **7.7.8 Unscheduled Visit**

An unscheduled visit is allowed at any time if in the investigator's opinion it is warranted. The following procedures may be performed at the Unscheduled Visit if required.

- LFGS assessments
- POL assessments
- pGAI assessment
- iGAI assessment
- Lip function evaluation
- Lip sensation evaluation

- Lip texture evaluation
- Lip firmness evaluation
- Lip symmetry evaluation
- Lip movement/function evaluation
- Vision Evaluation (Snellen visual acuity, confrontational visual fields, ocular motility)
- Assess AEs
- Swelling Assessment
- Subject Satisfaction with lips (VAS)
- Assess concomitant medications/treatments
- Complete CRFs

## **7.8 Efficacy Analysis**

### **7.8.1 Primary Efficacy Endpoint**

The primary efficacy endpoint is change from Baseline to Month 2 in overall lip fullness based on the Blinded Evaluating Investigator assessment using the LFGS. The LFGS is a validated scale (Carruthers et al, 2008).

### **7.8.2 Secondary Efficacy Analysis**

Secondary analysis include

- percent of subjects with treatment success (responder: overall LFGS based on the Blinded Evaluating Investigator Assessment) at Visit 3/Month 2 where responder is defined as a subject with at least a 1-grade increase from baseline on the LFGS post augmentation,
- percent of responders overall on the POL severity scale at Visit 4/Month 3 (defined as a subject demonstrating  $\geq 1$ -point improvement, i.e., decrease in severity, from baseline),
- change from baseline to Visit 4/Month 3 in overall LFGS based on the Blinded Evaluating Investigator Assessment
- change from baseline to Visit 5/Month 6 in overall LFGS based on the Blinded Evaluating Investigator Assessment.

### **7.8.3 Other Efficacy Analysis**

Other efficacy analysis include

- pGAI, iGAI, and Swelling Assessment at each scheduled visit,
- percent of subjects with treatment success (responder: upper lips, lower lips LFGS) at Visit 3/Month 2 where responder is defined as a subject with at least a 1-grade increase from baseline on the LFGS post augmentation
- percent of responders (upper lips, lower lips) on the POL severity scale at Visit 4/Month 3 (defined as a subject demonstrating  $\geq 1$ -point improvement, i.e., decrease in severity, from baseline),
- satisfaction with lips VAS at each scheduled visit,

- change from baseline to Visit 4/Month 3 and Visit 5/Month 6 in upper lips, lower lips LFGS.

## **7.9 Assessment of Safety**

### **7.9.1 Safety Analysis**

Safety of the study devices will be compared by evaluating the nature, severity, and frequency of treatment-emergent adverse events (TEAEs). All AEs that occur during the study will be recorded whether or not they are considered to be related to treatment. A description of the AE will be recorded with the date of onset, date of resolution, severity of the AE, relationship to the study device, action taken, and the outcome.

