## **6 STUDY OBJECTIVES**

To compare the safety and efficacy profile of PN40082 versus Restylane Silk for lip augmentation.

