### **8.4 Safety Analyses**

Adverse events will be coded to system organ class and preferred terms using the Medical Dictionary for Regulatory Activities (MedDRA, Version 20 or higher).

Frequency and percentage of subjects reporting treatment-emergent adverse events (TEAEs) will be tabulated for each treatment by preferred terms and further by severity and relationship to study device. In summaries of severity and relationship, subjects reporting more than one event in a treatment arm that are mapped to the same preferred term will be counted only once in that treatment arm under the strongest severity and relationship, respectively. In addition, visual related TEAEs will be summarized separately for each treatment by preferred term.

Assessment results of lip function, lip sensitivity, lip texture, lip firmness, lip symmetry, and lip movement/function will be summarized with frequency and percentage for each scheduled visit.

Safety analyses will be conducted using the ITT population.

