### **8.5 Sample Size Determination**

For the PRO 2018-02 study, the primary variable is change from baseline to Month 3 in LFGS. The sample size was determined based on (1) both PN40082 and Restylane Silk having an equal mean value with a common standard deviation of 0.85 for change from baseline in LFGS, and (2) the non-inferiority limit of -0.50. The test:control ratio of 1:1 results in 126 (63:63) PP subjects at 90% power. Assuming 80% of randomized subjects meet the PP criteria, a total of 158 (79:79) subjects will be randomized to obtain 126 (63:63) PP subjects.

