3.2 Sample Size Determination

For the PRO 2018-02 study, the primary variable is change from baseline to Month 3 in LFGS. The sample size was determined based on: (1) both PN40082 and Restylane Silk having an equal mean value with a common standard deviation of 0.85 for change from baseline in LFGS, and (2) the non-inferiority limit of -0.50. The test:control ratio of 1:1 results in 126 (63:63) per-protocol (PP) subjects at power of 90%. A total of 158 subjects will be randomized to obtain 126 (63:63) PP subjects assuming that 80% of randomized subjects meet the PP criteria.

4 Populations To Be Analyzed

Three subject populations are defined as follows:

- (1) As-treated (AT) (safety population): All randomized subjects who received study device. AT subjects will be included in the safety analysis for the treatment they actually received.
- (2) Modified intent-to-treat (mITT): All randomized subjects who met the inclusion/exclusion criteria, and received study device.
- (3) Per-protocol (PP): All randomized subjects who met all inclusion/exclusion criteria; received study device; completed Visit 5/Month 6 within the specified window; had overall LFGS score by the Blinded Evaluating Investigator at Visit 3/Month 2 within the specified visit window; and had no significant protocol violations that would affect the treatment evaluation.

For the purpose of determining the PP status of the subject, "significant protocol violations" are any unforeseen events that occurred during the conduct of the trial that result in noteworthy study protocol violations that could have possibly interfered with the therapeutic administration of the treatment or the precise evaluation of treatment efficacy.

Efficacy analyses will be performed on the mITT and PP populations, with PP as the primary population and mITT supportive. Analyses of safety and other evaluations will be performed on the AT population.

5 Planned Analyses

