5.5.2 Secondary Efficacy Analysis

The secondary efficacy endpoints include the following:

- percent of subjects with treatment success (responder on overall LFGS) at Visit 3/Month 2, where responder is defined as a subject with at least a 1-grade increase from baseline on the overall LFGS
- percent of responders on the overall POL severity scale at Visit 4/Month 3 (defined as a subject demonstrating ≥ 1 -point improvement, i.e., decrease in severity, from baseline)
- change from baseline to Visit 4/Month 3 in overall LFGS
- change from baseline to Visit 5/Month 6 in overall LFGS

The supporting importance of the secondary endpoints is ordered by [1] percent of subject with treatment success (responder on overall LFGS) at Visit 3/Month 2, [2] percent of responders on the overall POL severity scale at Visit 4/Month 3, [3] change from baseline to Visit 4/Month 3 in overall LFGS, and [4] change from baseline to Visit 5/Month 6 in overall LFGS.

These secondary variables will be summarized with descriptive statistics for each treatment arm and a 95% CI for the difference between treatments. For the proportion variables, the 95% CI for treatment difference will be calculated using the Wald's method, with subjects pooled from all study sites. For the change variables, the 95% CI for the median differences between treatments will be derived using PROC NPARIWAY with the option for the HL estimators.

For the mITT analysis, the LFGS-related secondary endpoints will be analyzed for each copy of the MI data sets. PROC MIANALYZE will then be performed to account for the between and within variation in the multiply imputed data sets.

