5.6.1 Adverse Events

All adverse events (AEs) occurring during the study will be recorded and coded in the Medical Dictionary for Regulatory Activities (MedDRA), version 20 or higher. TEAEs are defined as events that appear subsequent to the first injection or that were present prior to the first injection but worsened in intensity after the first injection.

Frequency and percent of subjects reporting TEAEs will be tabulated for each treatment by system organ class and preferred terms, and further by severity and relationship to study device. In summaries of severity and relationship, subjects who reported more than one event in a treatment arm that are mapped to the same preferred term will be counted only once in that treatment arm under the strongest severity and relationship, respectively.

TEAEs related to vascular injections/Visual events will also be tabulated by subject Fitzpatrick Skin Type (I-III vs. IV-VI), each Fitzpatrick Skin Type individually and by number of injections subjects received. Most frequently occurring TEAEs related to vascular injections/Visual events (those reported by 5% or more subjects of either treatment group) will be tabulated by preferred term. These TEAEs will also be summarized by event's severity and duration.

Treatment-Emergent Serious Adverse Events (TESAEs) and TEAEs that led to treatment interruption or discontinuation will be presented in data listings.

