5.6.3 Other Variables

Investigator Ease of Use Assessment

Overall ease of use of the device will be evaluated by the Treating Investigator using the numerical rating scale (NRS) from 0 being not easy to 10 being most easy at Visit 1/Day 1 and for subjects who have touch-up treatment at Visit 2/Month 1. It will be summarized for the AT subjects descriptively with mean, SD, minimum, median, and maximum.

Lip Evaluations

Lip function, lip sensation, lip texture, lip firmness, lip symmetry, and lip movement/function will be evaluated by the Blinded Evaluating Investigator at each visit. These variables will be summarized using frequency and percent of subjects by categories of incidence.

Concomitant Medications

Concomitant medications will be coded using the World Health Organization (WHO) Drug Dictionary, Version March 2013 or later, and will be presented in data listings.

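### Safety is to be compared between the devices, but no safety outcome gets a between-arm difference or a confidence interval

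*Protocol*

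**What the plan says.** The trial has a single objective, in Protocol Section 6: "To compare the safety and efficacy profile of PN40082 versus Restylane Silk for lip augmentation". Section 7.9.1 repeats the comparative intent for safety, without naming a statistic: "Safety of the study devices will be compared by evaluating the nature, severity, and frequency of treatment-emergent adverse events (TEAEs".

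The analysis sections describe tabulation by arm. Protocol Section 8.4: "Frequency and percentage of subjects reporting treatment-emergent adverse events (TEAEs) will be tabulated for each treatment by preferred terms". SAP Section 5.6.1: "Frequency and percent of subjects reporting TEAEs will be tabulated for each treatment by system organ class and preferred terms". For the lip evaluations, SAP Section 5.6.3 says: "These variables will be summarized using frequency and percent of subjects by categories of incidence". The TEAE shells (Tables 14.3.2.1 to 14.3.2.9 and 14.3.3.1 to 14.3.3.4) break events down by term, severity, causality and number of injections. For the vascular/visual set they add skin type, duration, outcome and action taken. The lip shells are Tables 14.3.4.1 to 14.3.4.7. All show the arms side by side, and none has a difference, ratio, interval or p-value.

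Secondary efficacy is handled differently in SAP Section 5.5.2: "These secondary variables will be summarized with descriptive statistics for each treatment arm and a 95% CI for the difference between treatments". Protocol Section 8.2 and SAP Section 5.1 call the comparisons on those endpoints descriptive and non-inferential.

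On numbers, Protocol Section 8.5 says "a total of 158 (79:79) subjects will be randomized to obtain 126 (63:63) PP subjects", and SAP Section 4 defines the safety set: "AT subjects will be included in the safety analysis for the treatment they actually received".

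**The concern.** Half of the only objective is a comparison of safety, and the plan supplies no comparative quantity for it. Descriptive status does not explain the omission, because the secondary efficacy endpoints have the same status and still get an interval.

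Two percentages printed next to each other do not tell a reader how large a true difference the data leave open. A gap that is only chance can be read as a signal, and a small gap can be read as reassurance. The sample size was set on the LFGS alone, so nothing else in the plan states the safety precision. The devices differ in hyaluronic acid concentration (25 v 20 mg/mL, Protocol Section 7.4.1), so relative local-reaction rates are a fair question. If contrasts are computed later, which ones and by which method would be chosen after the results are known.

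**Working it through.** **1. The plan's own figure.** Neither document gives a precision or power figure for safety. The only sizing is for efficacy: SD 0.85, limit -0.50, 90% power, two-sided 95% CI.

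- Per arm: 2 × (1.960 + 1.282)² × 0.85² / 0.50² = 60.7, so 61 by the normal formula and 62 by the t-test. The plan has 63, at which power is about 0.91.
- Randomized: 126 / 0.80 = 157.5, so 158, or 79 per arm. This agrees with the plan.

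The As-Treated set therefore has at most about 79 per arm.

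**2. Assumed event rates.** No rate is given for PN40082. The comparator rates below come from the Restylane Silk instructions for use reproduced in the protocol and are assumed in both arms.

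- Needle study MA-1700-04, TEAEs after first treatment: lip swelling 43%, contusion 44%, lip pain 10%, any TEAE 78%. For the last, the text prints 169/281, but the table has N = 218, and 169/218 = 77.5%.
- Cannula study 43USC1505, TEAEs: injection site swelling 13.3%, bruising 6.7%.
- Needle-study diary after first treatment: swelling 98%, tenderness 91%, bruising 81%.

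**3. Precision of a difference.** With equal observed rates p in both arms, the Wald 95% half-width is 1.96 × √(2p(1−p)/79). For p = 0.43: 2 × 0.43 × 0.57 / 79 = 0.006205; the root is 0.0788; times 1.96 gives 0.154.

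| Rate | Source | Wald, points | Newcombe, points |
|---|---|---|---|
| 43% | lip swelling | ±15.4 | ±15.1 |
| 44% | contusion | ±15.5 | ±15.1 |
| 78% | any TEAE | ±12.9 | ±12.8 |
| 10% | lip pain | ±9.4 | ±9.9 |
| 13.3% | swelling, cannula | ±10.6 | ±11.1 |
| 6.7% | bruising, cannula | ±7.8 | – |
| 81% | bruising, diary | ±12.2 | – |
| 91% | tenderness, diary | ±8.9 | – |
| 98% | swelling, diary | ±4.4 | – |

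The Wald maximum is ±15.6, at 50%, so the 15-point figure is close to the worst case.

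**4. How often chance produces a visible gap.** For two independent binomials of 79 with the same true rate, the exact probability of an observed gap of 10 points or more in either direction is 23% at 43%, 15% at 78%, and just under 5% at 10%.

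**The case against.** The strongest reply is that nothing here is contradictory. Section 7.9.1 says how safety is compared, and the shells do examine nature, severity and frequency in some detail. There is no safety hypothesis. The plan is tiered: the other efficacy variables, including upper- and lower-lip responder rates, also get descriptive statistics only (SAP Section 5.5.3). Descriptive safety tables are common practice, and any reader can form an interval from the printed n and N. An interval would show the imprecision without reducing it; a ±10-point half-width at 43% would need 189 per arm.

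Much of this stands. It makes the point an improvement to reporting and not an error. Two parts do not remove it. First, the other efficacy variables are not named in the objective, whereas safety is. Second, the printed tables do not allow every interval to be formed. Each TEAE table is either limited to vascular injection/visual events or excludes them, and a subject can appear in both, so an any-TEAE count cannot be obtained by adding them.

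A reader might infer that the plan intends to declare similar safety while differences of about 15 points remain open. The documents do not support that: they contain no such conclusion, margin or rule. Nor is 15 points a general figure. It applies to events near 43 to 44%, a rate taken from another study. Which comparator rate fits this trial is unsettled. Section 7.6.24 has subjects record any AE in the diary, and the adverse-event listing shell has a diary-reported example. Section 7.9.8 leaves the recording of persisting diary events as AEs to the investigator.

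**Conclusion.** The point holds as an inexpensive improvement. The objective and Section 7.9.1 promise a safety comparison, and no between-arm safety estimate or interval is planned in the protocol, the SAP text or the shells. The consequence is limited to this: whatever comparison is reported will lack an estimate and a statement of precision.

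The precision at stake is about 15 points for events near 43 to 44%, 13 at 78%, 9 to 11 at 10 to 13%, and 4 to 12 at diary rates of 98 to 81%. These figures assume 79 treated subjects per arm and comparator label rates in both arms. They describe what the trial could exclude and say nothing about whether the devices differ.

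**What to change.** In Protocol Section 8.4 and SAP Section 5.6.1, add the difference in percentage of subjects, PN40082 minus Restylane Silk, with a 95% CI by the Miettinen-Nurminen or Newcombe method. Both methods cope with zero cells. Use the As-Treated set; Protocol Section 8.4 still names the ITT population and should be brought into line with the SAP. Fix the list in advance:

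- any TEAE;
- any related TEAE (possibly or probably);
- any moderate or severe TEAE;
- each preferred term reported by 5% or more of subjects in either arm.

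State that the intervals are descriptive and unadjusted for multiplicity, and quote them where the report compares safety.

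The cost is one small new summary table, not just a column in existing ones. It must pool the two event sets, because no current shell has an any-TEAE or a moderate-or-severe row across both, and the 5% tables exist only for the vascular/visual set. It brings several unadjusted intervals that need cautious reading. No additional subjects, visits or data are required.
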